Appendix F Dose Modification and Supportive Care Guidelines for Atezolizumab

As of May 2015, atezolizumab has been administered to approximately 3200 patients with solid tumors and hematologic malignancies. In addition to studies presented in the previous sections, safety information for atezolizumab is also gleaned from studies in the entire development program, including those where atezolizumab is investigated in combination with other unapproved agents.

Study PCD4989g, in which atezolizumab is being used as a single agent in patients with locally advanced or metastatic solid tumors or hematologic malignancies, provides the majority of data (with 558 safety evaluable patients as of the data extraction date of 11 May 2015) for the safety profile of atezolizumab as monotherapy. Currently, no maximum tolerated dose, no dose-limiting toxicities and no clear dose-related trends in the incidence of AEs have been determined.

In trials investigating the combinations of atezolizumab with bevacizumab and/or chemotherapies, cobimetinib, or vemurafenib, the incidence of AEs in the treatment arms with combined use was consistent with the known safety profiles of the individual study drugs. Fatigue, decreased appetite, nausea and cough were commonly reported adverse events in single and combination therapy. The overall immune mediated adverse events reported for atezolizumab were considered moderate in severity and majority of patients were able to continue on atezolizumab therapy.

Although most immune-mediated adverse events observed with immunomodulatory agents have been mild and self-limiting, such events should be recognized early and treated promptly to avoid potential major complications.³⁹ A summary of identified risks for atezolizumab is presented in Appendix Table 3.

Appendix Table 3 Summary of Identified Risks of Atezolizumab

Identified Risk	Description of Risk
Colitis	Serious reports of biopsy confirmed colitis have been reported in less than 0.5% of patients who received single agent atezolizumab. The events were of Grade 2 or 3 in severity and the majority of reported colitis resolved following treatment. Patients continued to receive atezolizumab despite the event. Diarrhea (19.7%) has been reported with single agent atezolizumab. These events were considered mild to moderate and resolved without treatment.
Dermatologic reactions	Dermatologic reactions have been reported in 42% of patients receiving single agent atezolizumab. Reactions have been mild to moderate (<1% reported as severe). Commonly reported events in PCD4989g include rash (15%), pruritus (13%), dry skin (7%), maculopapular rash (6%), night sweats (6%) and erythema (3%). Alopecia, dermatitis acneiform, dermatitis psoriaiform, vitiligo, seborrheic dermatitis, lichen planus, bullous dermatitis and skin pigmentation changes have also been reported less commonly.
Endocrine disorders	Adrenal insufficiency has been observed in 0.2% of patients receiving single agent atezolizumab, and in <2% of patients receiving atezolizumab in combination with other chemotherapy. Associated laboratory parameters such as hyponatremia and hypokalemia were observed in <1 % of patients receiving single agent atezolizumab, and hyponatremia was observed in 1.6% of patients receiving atezolizumab in combination with chemotherapy. Hypothyroidism events have been reported in up to 6% of patients receiving atezolizumab across the clinical program. The majority of events were reported in patients receiving single agent atezolizumab. Events have generally been mild and patients who received treatment with thyroid replacement were able to continue on study treatment. Hyperthyroidism events have occurred in 0.7% of patients receiving single agent atezolizumab. The majority of patients with hyperthyroidism appear to be asymptomatic. Patients received treatment with anti-thyroid agents and were continued on study treatment.
Hepatitis	In patients receiving atezolizumab as a single agent, hepatitis and elevations of alkaline phosphatase, AST and ALT have been reported in 0.5%, 4.1%, 6.1% and 5.6% of patients, respectively. In the clinical program, <1% of patients experienced serious adverse events of hepatobiliary disorders including autoimmune hepatitis (5), hepatitis (3), and the following (1 patient each): drug induced liver injury, hepatic failure, abnormal hepatic function, hepatocellular injury, and liver disorder.
Hypersensitivity	Hypersensitivity reactions including allergic and anaphylactic reactions have been reported in <1% of patients receiving single agent. Outcomes for these events were considered resolved. Patients may present with complaints such as flushing, fever, chills, blood pressure change, tachycardia or shortness of breath
Influenza-like illness	Influenza like illness has been reported in patients receiving atezolizumab as a single agent in PCD4989g (7.3%). Events associated with influenza like illness were primarily observed one to two weeks after receiving the first cycle. Reactions have included fever, fatigue, asthenia, chills, myalgia, arthralgia and headache. The events have been mild to moderate in severity.

Identified Risk	Description of Risk
Infusion-related reactions	Symptoms may present within 30 minutes to 24 hours after infusion, are generally mild and manageable, and wane with subsequent infusions. With single agent atezolizumab, IRRs have been reported in 0.4% of patients. The most common symptoms reported with single agent use within 24 hours of the first cycle were pyrexia, fatigue, nausea, hypertension, headache and diarrhea.
Neurologic disorders	Myasthenia gravis and Guillain-Barré syndrome have been observed in less than 1% of patients taking atezolizumab. Patients may present with signs and symptoms of sensory and/or motor neuropathy. Meningitis (non-infectious) has also been reported in <1% of patients. Patients with meningitis may present with altered mental status, confusion, headache, or fever. Diagnostic work-up is essential for an accurate characterization to differentiate between alternate etiologies.
Pneumonitis	Pneumonitis has been reported in 1.4% of patients receiving single agent atezolizumab. These events have been primarily observed in patients with lung cancer. Four fatal reports of pneumonitis have been reported. Patients may present with dyspnea, hypoxia or other respiratory complication. Diagnostic work-up is essential for an accurate characterization to differentiate between alternate etiologies such as infection, pulmonary embolism or underlying disease.

ALT=alanine transaminase; AST=aspartate transaminase; IRR=infusion-related reactions.

Note: This table is based on single agent data from Study PCD4989g as of the data extraction date of 11 May 2015 in 558 treated patients. The information is also based on a review of safety information across the atezolizumab development program as of the cutoff date for this version of the IB. Single-agent studies include GO28753, GO28754, GO28625, GO28915 and GO29293. Combination studies include WO29074, GO29322, and GP28328.

When the IB is used as the Reference Safety Information, the Appendix Table 4 provides a list of the adverse drug reactions (ADRs), which are considered “expected” for regulatory reporting purposes by the Sponsor. Descriptions of the risks associated with each of the listed ADRs are summarized in Appendix Table 3, including population exposed to the IMP, and intensity and frequency of the risk (where available).

The classification of an AE as an ADR is based on data available at the time of assessment. Data obtained at later dates may refute the connection between an AE and atezolizumab, and lead to an ADR being subsequently reclassified as an AE. Guidelines for management of these events are provided above.

Appendix Table 4 Expected Adverse Drug Reactions for Atezolizumab in All Indications for Regulatory Reporting Purposes Only

Risk	Notes/Exclusions
Gastrointestinal Disorders	Includes colitis, diarrhea, dysphagia, nausea, vomiting, abdominal pain and decreased appetite
Dermatologic reactions	Includes rash and pruritus
Endocrine disorders	Includes hyperthyroidism, hypothyroidism and adrenal insufficiency
Hepatitis^a	Includes ALT increased, AST increased, and hepatic enzymes abnormal
Hypersensitivity reactions/ Infusion-related Reactions	
Influenza-like illness	Includes arthralgia, musculoskeletal pain, asthenia, chills, fever, fatigue, and nasal congestion
Nervous system disorders	Includes meningitis, Guillain-Barré syndrome, myasthenic syndrome
Pneumonitis^a	Includes dyspnea and hypoxia
General and Metabolic disorders	Includes hyponatremia , hypokalemia, and insomnia
Vascular disorders	Includes hypertension and hypotension

^a Includes fatal events.

Note: Any term covered by the medical concepts presented in this list is considered “expected” for both non-serious and serious reports of suspected unexpected ADRs to Health Authorities, excluding events with fatal outcome unless detailed otherwise in the table.

The classification of an AE as a potential risk is based on the mechanism of action of atezolizumab, pre-clinical findings, as well as other agents with similar mechanisms of action. As of the cutoff date for the data included below, the safety profile remains consistent based on the known mechanism of action of atezolizumab. The potential risks associated with atezolizumab are summarized in Appendix Table 5, followed by guidelines for the management of these atezolizumab-specific AEs.

Dyspnea, cough, fatigue, hypoxia, pneumonitis and pulmonary infiltrates have been associated with the administration of atezolizumab and have primarily been observed in patients with underlying NSCLC.

Mild to moderate events of pneumonitis have been reported with atezolizumab. All pulmonary events should be thoroughly evaluated for other commonly reported etiologies such as pneumonia/infection, lymphangitic carcinomatosis, pulmonary embolism, heart failure, or chronic obstructive pulmonary disease, or pulmonary hypertension:

- Measurement of oxygen saturation (i.e., arterial blood gas)
- High-resolution CT scan of the chest
- Bronchoscopy with bronchoalveolar lavage and biopsy
- Pulmonary function tests (diffusion capacity of the lung for carbon monoxide [DL_{CO}])
- Pulmonary function testing with a pulmonary embolism protocol

Patients will be assessed for pulmonary signs and symptoms throughout the study. Patients will also have CT scans of the chest at every tumor assessment.

Appendix Table 6 Guidelines for Management of Atezolizumab-Associated Pulmonary Toxicity

Pulmonary Events/ Pneumonitis	Severity	Management
	Grade 1	
 • May continue atezolizumab with close monitoring • Re-evaluate on serial imaging • Consider pulmonary consultation
	Grade 2	
 • Withhold atezolizumab • Pulmonary and ID consultation with consideration for bronchoscopy/BAL • Start 60 mg prednisone or equivalent per day • When improves to Grade 0 or Grade 1, then taper steroids over ≥ 1 month • Atezolizumab may be resumed if the event improves to Grade 0 or 1 within 12 weeks and corticosteroids have been reduced to the equivalent of oral prednisone 10 mg daily or less. • Treat as Grades 3-4 if recurrent episode of pneumonitis
	Grade 3 and 4	
 • Permanently discontinue atezolizumab • Bronchoscopy/BAL is recommended • Start 60 mg prednisone or equivalent per day. • Taper steroids over ≥ 1 month once symptoms improve to Grade 0 or 1. • If not improving after 48 hours or worsening: add additional immunosuppression (e.g., infliximab, cyclophosphamide, IVIG, or mycophenolate mofetil) • Contact Medical Monitor if atezolizumab is discontinued

BAL=bronchoscopic alveolar lavage; ID=infectious diseases; IVIG=intravenous immunoglobulin

Hepatic Events

Immune-mediated hepatitis has been associated with the administration of atezolizumab. Eligible patients must have adequate liver function, as manifested by measurements of total bilirubin and hepatic transaminases, and liver function will be monitored throughout study treatment.

While in this study, patients who present with right upper-quadrant abdominal pain and/or unexplained nausea or vomiting should have liver function tests (LFTs) performed immediately and reviewed before administration of the next dose of study drug.

If LFTs increase, concurrent medications, viral hepatitis, and toxic or neoplastic etiologies should be considered and addressed, as appropriate. Imaging of the liver, gall bladder, and biliary tree should be performed to rule out neoplastic or other causes for increased LFTs. Anti-nuclear antibody, perinuclear anti-neutrophil cytoplasmic antibody, anti-liver kidney microsomal

antibodies, and anti-smooth muscle antibody tests should be performed if an autoimmune etiology is considered.

Appendix Table 7 Management Guidelines for Hepatic Events

Hepatic events	Severity	Management
	Grade 1	
 • Continue therapy • Continue LFT monitoring
	Grade 2	
 • Monitor LFTs more frequently until return to baseline values • If persists $\geq 5-7$ days: withhold therapy and start 60 mg prednisone or equivalent per day; when LFTs are \leq Grade 1, taper steroids over ≥ 1 month, resume therapy if the event improves to Grade 0 or Grade 1 within 12 weeks and systemic steroid dose is ≤ 10mg oral prednisone equivalent per day
	Grade 3 and 4	
 • Discontinue therapy • Consider GI consult and liver biopsy to establish etiology of hepatic injury if necessary • Start 60 mg prednisone or equivalent per day • If LFT results do not decrease within 48 hours after initiation of systemic steroids, addition of an alternative immunosuppressive agent (e.g., mycophenolate or TNF-α antagonist) may be considered. • Taper steroids over ≥ 1 month, when symptoms improve to Grade 0 or 1 • Contact Medical Monitor if atezolizumab is discontinued

GI=gastrointestinal; LFT=liver function test; TNF- α =tumor necrosis factor alpha.

Gastrointestinal Events

Immune-mediated colitis has been associated with the administration of atezolizumab.

If the event is of significant duration or magnitude or is associated with signs of systemic inflammation or acute phase reactants (e.g., increased C-reactive protein, platelet count, or bandemia), the following are recommended:

- Perform sigmoidoscopy (or colonoscopy, if appropriate) with colonic biopsy with 3 to 5 specimens for standard paraffin block to check for inflammation and lymphocytic infiltrates for confirmation of the diagnosis of colitis. If possible, one or two biopsy specimens should be snap-frozen and stored.
- Perform laboratory tests to rule out alternate etiology (i.e., WBCs and stool calprotectin).

Appendix Table 8 Management Guidelines for GI Events (Diarrhea/ Colitis)

GI Events (Diarrhea/Colitis)	Severity	Management
	Grade 1 diarrhea or colitis	
 • Continue therapy • Symptomatic treatment • Endoscopy is recommended if symptoms persist for greater than 7 days. • Close monitoring
	Grade 2 diarrhea or Grade 2 colitis	
 • Withhold atezolizumab • Symptomatic therapy • GI consultation recommended • If persists  5 days or recurs: Prednisone 60 mg/day or equivalent • Taper steroids over  1 month when symptoms improve to Grade 0 or 1 • Treatment may be resumed if the event improves to Grade 0 or 1 within 12 weeks and corticosteroids have been reduced to the equivalent of prednisone 10 mg PO daily or less.
	Grade 3 diarrhea or colitis	
 • Withhold atezolizumab • GI referral and confirmation biopsy • Treat with IV steroids (1-2 mg/kg/day methylprednisolone or equivalent) and convert to oral steroids (prednisone 60 mg/day or equivalent) after improvement • When improves to Grade 0 or 1, then taper steroids over \geq 1 month • Treatment may be resumed if the event improves to Grade 0 or 1 within 12 weeks and corticosteroids have been reduced to the equivalent of oral prednisone 10 mg daily or less.
	Grade 4 diarrhea or colitis	
 • Discontinue atezolizumab • GI referral and confirmation biopsy • Treat with IV steroids (1-2 mg/kg/day methylprednisolone or equivalent) and convert to oral steroids (prednisone 60 mg/day or equivalent) once improvement • When patient's diarrhea or colitis improves to Grade 0 or 1, then taper steroids over \geq 1 month • If not improving after 48h of initiating steroids or worsening, addition of an alternative immunosuppressive agent (e.g., mycophenolate or TNF-α antagonist) may be considered. • Contact medical monitor if atezolizumab is discontinued.

GI=gastrointestinal; PO=per oral; TNF- α =tumor necrosis factor alpha.

Endocrine Events

Thyroid disorders or adrenal insufficiency has been associated with the administration of atezolizumab.

Patients with unexplained symptoms such as fatigue, myalgias, impotence, mental status changes, or constipation should be investigated for the presence of thyroid, pituitary, or adrenal endocrinopathies, as well as for hyponatremia or hyperkalemia. An endocrinologist should be consulted if an endocrinopathy is suspected. TSH and free thyroxine (T4) levels should be obtained to determine whether thyroid abnormalities are present. TSH, prolactin, and a morning cortisol level will help to differentiate primary adrenal insufficiency from primary pituitary insufficiency.

Appendix Table 9 Management Guidelines for Endocrine Events

Endocrine Events	Severity	Management
	Asymptomatic hypothyroidism	
 Continue atezolizumab Start thyroid replacement hormone Monitor TSH weekly
	Symptomatic hypothyroidism	
 Withhold atezolizumab Start thyroid replacement hormone Consider referral to an endocrinologist Restart atezolizumab when symptoms are controlled by thyroid replacement and TSH levels are decreasing
	Asymptomatic hyperthyroidism	
 If serum TSH \square 0.5mU/L, repeat with free T4 and T3 to diagnose asymptomatic hyperthyroidism If confirmed, and in the absence of symptoms, continue atezolizumab and repeat tests in 4 weeks If thyroid values remain stable and patient is asymptomatic, follow lab results monthly Hold atezolizumab if TSH \square \leq 0.1mU/L or if patient develops symptomatic hyperthyroidism Consider referral to an endocrinologist and treat according to symptomatic hyperthyroidism guidelines
	Symptomatic hyperthyroidism	
 Withhold atezolizumab Start methimazole as needed Consider referral to an endocrinologist Restart atezolizumab when symptoms are controlled by thyroid replacement Permanently discontinue atezolizumab for life threatening immune-mediated hyperthyroidism.

Endocrine Events (cont.)	Severity	Management
	Symptomatic pan-hypopituitarism and any Grade 3-4 events	
 • Discontinue atezolizumab. • Endocrinologist consultation • Perform appropriate imaging. • Treat with an initial dose of methylprednisolone 1–2 mg/kg per day IV followed by oral prednisone 1–2 mg/kg per day. • Start steroid taper when symptoms improve to Grade 0 or Grade 1. Taper over > 1 month. • Patients with unexplained symptoms such as fatigue, myalgia, impotence, mental status changes, or constipation should be investigated for the presence of thyroid, pituitary, or adrenal endocrinopathy as well as for hyponatremia or hyperkalemia. An endocrinologist should be consulted if a symptomatic endocrinopathy is suspected. TSH and free T4 levels should be obtained to determine whether thyroid abnormalities are present. TSH, prolactin, and a morning cortisol level will help to differentiate primary adrenal insufficiency from primary pituitary insufficiency. • Contact the Medical Monitor if atezolizumab is discontinued.

T4=thyroxine; TSH=thyroid stimulating hormone.

Ocular Events

An ophthalmologist should evaluate visual complaints. Uveitis or episcleritis may be treated with topical corticosteroid eye drops. Atezolizumab should be permanently discontinued for immune-mediated ocular disease that is unresponsive to local immunosuppressive therapy.

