5.4.3 Toxicities Associated with Atezolizumab

Atezolizumab will be withheld until resolution (i.e., return to Grade 0-1) for the following event(s):

- Grade ≥ 2 pneumonitis
- Grade ≥ 3 symptomatic hepatic toxicities that do not resolve to Grade 2 within 48 hours or Grade ≥ 3 asymptomatic hepatic toxicities that do not resolve to Grade ≤ 1 within 3 weeks of onset with the following exceptions:
 - For patients with Grade 2 AST, ALT, alkaline phosphatase abnormality at baseline, an increase to $>8\times$ the upper limit of normal (ULN) that does not resolve to Grade 2 within 48 hours (if symptomatic) or Grade ≥ 3 asymptomatic hepatic toxicities that do not resolve to Grade ≤ 1 within 3 weeks of onset (if asymptomatic) will be considered a DLT.
- Grade ≥ 2 diarrhea or colitis
- Symptomatic hypothyroidism, hyperthyroidism, pan hypopituitarism, or any Grade ≥ 3 endocrine events
- Grade ≥ 3 ocular events
- Grade ≥ 3 dermatologic events
- Grade ≥ 2 neuropathy
- Grade ≥ 4 neutropenia (absolute neutrophil count [ANC] $<500/\mu\text{L}$) lasting ≥ 7 days, thrombocytopenia, anemia, or Grade ≥ 3 febrile neutropenia
- Grade ≥ 3 non-hematologic, non-hepatic organ toxicity, excluding the following:
 - Grade 3 immune related AE (irAE) that resolves to Grade ≤ 1 within 3 weeks of its onset (may include events that resolve after medical treatment, including immunosuppressant therapy)
 - Grade 3 nausea or vomiting that resolves to Grade ≤ 1 within 72 hours of appropriate supportive therapy
 - Grade ≥ 3 fatigue that resolves to Grade ≤ 2 within 7 days
 - Grade 3 arthralgia that can be adequately managed with supportive care or that resolves to Grade ≤ 2 within 7 days

- Grade 3 fever (in the absence of any clinically significant source of fever) that resolves to Grade ≤ 2 within 7 days with supportive care
- Grade ≥ 3 laboratory abnormality that is asymptomatic and deemed by the Investigator not to be clinically significant
- Grade 3 tumor flare defined as local pain, irritation, or rash localized at sites of known or suspected tumor
- Grade 3 infusion reaction that resolves within 6 hours to Grade ≤ 1

These reactions, along with any DLTs, will be reviewed by the DMC on a case-by-case basis and may be considered DLTs if they meet the criteria outlined above. Atezolizumab treatment can be resumed in patients whose adverse reactions recover to Grade 0-1.

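### Appendix Table 9: in the symptomatic hyperthyroidism row, the condition for restarting atezolizumab names a treatment that the row never starts (internal inconsistency, minor)

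*Protocol*

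**What the plan says.** Appendix Table 9 of the Protocol (Management Guidelines for Endocrine Events, in Appendix F) treats the thyroid disorders row by row.

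- **Symptomatic hyperthyroidism, treatment steps:** "Withhold atezolizumab Start methimazole as needed Consider referral to an endocrinologist".
- **Symptomatic hyperthyroidism, restart condition:** "Restart atezolizumab when symptoms are controlled by thyroid replacement". Read on into the discontinuation step, which identifies the row: "Restart atezolizumab when symptoms are controlled by thyroid replacement Permanently discontinue atezolizumab for life threatening immune-mediated hyperthyroidism".
- **Symptomatic hypothyroidism:** "Start thyroid replacement hormone Consider referral to an endocrinologist Restart atezolizumab when symptoms are controlled by thyroid replacement and TSH levels are decreasing".
- **Asymptomatic hyperthyroidism:** for patients whose course calls for it, the row says to "treat according to symptomatic hyperthyroidism guidelines", so it leads into the row at issue.

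Two other places bear on the point. Appendix Table 3 says of hyperthyroidism: "Patients received treatment with anti-thyroid agents and were continued on study treatment". It mentions thyroid replacement only under hypothyroidism. Section 5.4.3 lists both symptomatic hypothyroidism and hyperthyroidism among the events for which atezolizumab is withheld, and closes with a general rule: "Atezolizumab treatment can be resumed in patients whose adverse reactions recover to Grade 0-1". The synopsis entry on atezolizumab toxicities gives the same list and the same rule.

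**The concern.** A restart condition normally refers back to the treatment given for the event. In the symptomatic hyperthyroidism row it refers instead to the treatment for the opposite disorder. A site applying the row has to work out what the condition was meant to be.

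Appendix F is operative text. The synopsis (Safety Monitoring) and Section 7.2.2 both require study treatment to be withheld as that appendix sets out, and both arms receive atezolizumab. What is at stake is a clear and uniform rule for resuming drug across up to 20 sites (Section 5.1). If sites replace the line with their own criterion, those criteria may differ.

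The Grade 0-1 rule in Section 5.4.3 and the synopsis adds a second difficulty: the Protocol does not say how that general rule and the event-specific restart lines of Table 9 fit together.

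**Working it through.** The main check is a comparison of texts. The only arithmetic is the expected number of cases.

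**1. The row against itself and its neighbour**

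| Appendix Table 9 row | Treatment started | Restart condition refers to |
|---|---|---|
| Symptomatic hypothyroidism | Thyroid replacement hormone | Thyroid replacement, plus falling TSH |
| Symptomatic hyperthyroidism | Methimazole, as needed | Thyroid replacement |

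In the hypothyroidism row the treatment and the condition agree. In the hyperthyroidism row they do not. The restart phrase is the same in both rows as far as the word replacement. The hyperthyroidism line is the one followed by the instruction on permanent discontinuation for life-threatening hyperthyroidism, and only that line is in question. The shared phrase suggests carry-over from the other row, but the documents do not state the cause.

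**2. The row against Appendix Table 3**

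Appendix Table 3 pairs hypothyroidism with replacement and hyperthyroidism with anti-thyroid agents. That agrees with the treatment step of the hyperthyroidism row and disagrees with its restart line.

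**3. Table 9 against Section 5.4.3 and the synopsis**

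The general rule is recovery to Grade 0-1. Table 9 asks for symptom control on a named treatment, with a TSH clause for hypothyroidism. The two are worded differently for both symptomatic thyroid rows. This gap is therefore separate from the mismatch in step 1 and is not evidence for it.

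**4. Expected number of cases**

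Inputs: 0.7% hyperthyroidism on single-agent atezolizumab, with most patients asymptomatic (Appendix Table 3); about 80 patients, 40 per arm (synopsis).

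- Any hyperthyroidism: 0.007 × 80 = 0.56 expected. Chance of at least one case: 1 − 0.993^80 ≈ 0.43.
- Symptomatic: if most are asymptomatic, fewer than half are symptomatic, so the rate is below 0.007 / 2 = 0.0035. Expected: below 0.0035 × 80 = 0.28. Chance of at least one case: below 1 − 0.9965^80 ≈ 0.24.

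Some asymptomatic patients may later come under the symptomatic row. The documents give no rate for this. If every hyperthyroid patient did so, the figure would return to 0.56, so 0.56 is the ceiling on use of the row at the stated rate.

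**The case against.** The strongest reply is that the line is unlikely to mislead anyone treating a real patient. Methimazole is given only as needed. The row offers referral to an endocrinologist, and the endocrine text of Appendix F says one should be consulted when an endocrinopathy is suspected. Section 7.2.2 and Appendix F place toxicities under standard medical practice, and Appendix F asks for a benefit-risk judgement before further dosing. Appendix Table 3 names the class of agent used for hyperthyroidism.

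Most of this stands, and it limits how far the point can be taken. A reader might infer any of the following, and the documents support none of them:

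- **That the restart condition can never be met, or misdirects every time it is used.** The as-needed wording and the referral step leave room for judgement, so this goes too far.
- **That the Protocol orders thyroid replacement for hyperthyroid patients.** It does not. The phrase qualifies when to restart; it is not a treatment step.
- **That three rules conflict in this row alone.** The Grade 0-1 rule is general and differs from the hypothyroidism row as well.
- **That 0.56 is the expected number of affected patients.** That figure covers all hyperthyroidism, and Appendix Table 3 says most cases were asymptomatic.

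What the reply does not do is repair the line. Without methimazole, the condition still names a treatment that the row never starts. If a later move to replacement was intended for some patients, the row does not say so. The wording is legible and unredacted. The sentence calling recommendations suggested guidance only follows Appendix Table 15 and concerns systemic immune activation, not Table 9.

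**Conclusion.** The restart line in the symptomatic hyperthyroidism row is wrong as written. It conflicts with the treatment step of its own row and with Appendix Table 3, and no other part of the Protocol corrects it. It is an internal inconsistency, not a debatable design choice, and it is minor. The difference between Table 9 and the Grade 0-1 rule is real but separate, and it applies to both symptomatic thyroid rows.

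Fewer than about 0.28 symptomatic cases are expected in 80 patients. This rests on the single-agent rate holding in the combination arm, for which the documents give no rate, and on taking the statement that most cases were asymptomatic to mean that fewer than half were symptomatic. It does not count asymptomatic patients who later come under the row.

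The consequence is possible uncertainty or inconsistency between sites in resuming atezolizumab. No endpoint, analysis population, sample size, error rate or planned analysis is affected.

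**What to change.** The sponsor should reconcile the restart line of the symptomatic hyperthyroidism row in Appendix Table 9 with the treatment named in that row and with Appendix Table 3. In the same edit, the restart wording of both symptomatic thyroid rows should be reconciled with the Grade 0-1 rule in Section 5.4.3 and the synopsis, so that sites can tell how the two relate. This review does not say which criterion is right and does not propose one.

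The cost is one line in the appendix, plus a short clarification of how the appendix and Section 5.4.3 fit together. The SAP needs no change.
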